3.2 Subject Compliance

If a subject consistently reports failing to drink at least 80% of the beverages, or fails to show up for the weekly visit multiple times, they will be dropped from the study. At the weekly visits, study staff will weigh the returning supplement containers and write the mass on the container.

This will allow for calculation of expected decrease in mass over time, which will provide data as to subject compliance.

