1.0 Background and Rationale

Heart failure develops when cardiac muscle becomes weakened and consequently is compromised in its ability to contract, relax, or both. Impaired heart function leads to reduced exercise capacity, which in turn leads to progressive muscle weakness and a vicious cycle of sedentary behavior, weight gain, and subsequent development of metabolic abnormalities and sarcopenia. Approximately 6-10% of individuals over the age of 65 suffer from heart failure (1). The risk of death is 35% in the first year after diagnosis, and decreases to about 10% per year thereafter (2). There are two principal forms of heart failure. Most commonly, heart failure has referred to reduced force of ejection (systolic heart failure). Heart failure may also result from an impaired ability of the heart to relax (diastolic heart failure) (3). Systolic heart failure is often accompanied with diastolic dysfunction (1-2). However, more often the contractile capacity of the heart is not affected, or only slightly impaired, and thus (unlike the case with systolic heart failure) the ejection fraction is usually preserved. This form of heart failure is termed heart failure with preserved ejection fraction (HFPEF), and is the predominant form of heart failure world-wide (4,5). Not only are there different types of heart failure, there is a wide range of potential causes of heart failure, including the natural process of aging (6). Regardless of the specific underlying cause or type of heart failure, there are common pathophysiological responses. Most prominently, impaired exercise capacity, shortness of breath, fatigue and muscle strength are hallmarks of heart failure that lead to decreased physical function, and ultimately sedentary behavior and development of insulin resistance (2). Heart failure is also associated with fluid retention and even edema of the intestinal wall which resultant malabsorption of nutrients (7). Poor health of the intestinal mucosa in heart failure might potentially also influence the gut microbiome. Some long-term consequences of reduced exercise tolerance and malabsorption in long-standing heart failure are loss of muscle mass and the development of cardiac cachexia (7). These responses not only contribute to morbidity and mortality and financial strain on the health care system, but to decreased health-related quality of life.

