3.0 Study Design and Procedures

This is a randomized, double blind, prospective study examining the effects of 12 weeks' ingestion of either EAA mixture or placebo on physical function. We will also examine several blood parameters and fecal microbiome in both groups of subjects (see section 5.1). Up to 80 subjects ages 60 to 89 will be enrolled to obtain 60 completers (30 per group).

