If not performed at visit 1, the physical exam will be performed at this visit. Randomization will be performed as mentioned below. The following assessments will be performed: functional (6-minute walk distance), SF-36 health questionnaire, a whole-body DEXA scan for lean mass measurement, strength (Cybex testing of maximal voluntary contraction of each leg; bilateral hand grip strength). Subjects will be provided with forms and training for recording their dietary intake over a 3-day period during the next week. Study staff will dispense approximately 10 days' worth of study product and a consumption diary for subjects to complete after ingesting each dose. Future visits will be scheduled.

Visits 3-7: Subjects will come to the IOA weekly to return their urine samples, empty supplement containers and consumption diary. They will be asked about any adverse events since last visit. Study staff will dispense more study product and a consumption diary.

Visit 8: Subjects will be asked about any adverse events since last visit. They will return their empty supplement containers and consumption diary. In no particular order, the following assessments will be performed: strength (Cybex testing of maximal voluntary contraction of

each leg; bilateral hand grip strength), functional (6-minute walk distance), SF-36 health questionnaire. Study staff will dispense more study product, a consumption diary, and another 3-day diet diary.

Visits 9-12: Subjects will come to the IOA weekly to return their empty supplement containers and consumption diary. They will be asked about any adverse events since last visit. Study staff will dispense more study product and a consumption diary.

Visit 13: Subjects will come to the IOA to return their empty supplement containers and consumption diary. They will be asked about any adverse events since last visit. Study staff will dispense more study product and a consumption diary. Subjects will be provided with a drink containing 30mg of a stable isotope of creatine (D-3, Cambridge Isotopes Laboratory, Tewksbury, MA). They will be asked to collect 3 separate urine samples over the next 48 hours at approximately 24-hour intervals and return them to UAMS at their next visit. Subjects will be issued a stool sample collection kit to use just prior to visit 14 and another 3-day diet diary.

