Visit 14: Subjects must come to this visit having fasted overnight. They will be asked about any adverse events since last visit. They will return their diet records, empty supplement containers, any full supplement containers, their stool sample, and their consumption diary. Study staff will administer and score the SLUMS test for dementia. A fasting blood sample (~30 mL) will be drawn. After the blood sample is drawn, subjects will be offered a meal and beverages. A urine sample will be collected for dipstick proteinuria.

The following assessments will be performed: functional (6-minute walk distance), SF-36 health questionnaire, a whole-body DEXA scan for lean mass measurement, strength (Cybex testing of maximal voluntary contraction of each leg; bilateral hand grip strength). At the end of this visit, subject will have no further study visits.

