3.5 Blinding

This is a double-blinded study. EAA mixture will be provided by Prinova Inc. (Carol Stream, IL). Placebo will be purchased from online or local sources (Pure Protein website, Wal-Mart, etc.). Product containers will be coded so that only the unblinded study staff will know product

identity. After all study visits have been performed and all data entered into a database, the blind will be broken. Although the study products differ in taste, subjects will not be told which products are offered in which flavors.

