3.6 Study Products

The active study product is 9g twice a day of EAA mixture, a proprietary formula of Essential Blends, LLC (Fairbanks, AK). Product is a blend of amino acids, flavorings, caffeine and sweeteners (see Appendix) in powder form; packaged in 200g sealed containers. Subjects will dissolve 1 scoop of supplement into ~7 ounces of water and stir/shake until fully dissolved. They will be provided with shaker cups free of charge. Servings will be ingested between meals so that they ingest 2 servings per day. EAA mixture is currently available in only one flavor (lemon/lime).

The placebo product is 9g twice a day of Pure Protein 100% Whey protein (Worldwide Sport Nutritional Supplements, Inc., Bayport, NY). Unblinded study staff will repackage this product into 200g sealed containers which contain the appropriate scoops. See appendix for product information. Subjects will dissolve 1 scoop of supplement into ~7 ounces of water and stir/shake until fully dissolved. Servings will be ingested between meals so that they ingest 2 servings per day.

Subjects will be asked to save empty containers and return them to the study site for accountability purposes. Storage of both products is in a dry area at room temperature. Containers will be labelled identically, with the only difference being the study product code (A or B); the key to which is known only to the unblinded study staff until blinding has been broken at the end of data analysis.

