4.0 Study Population

Subjects will be recruited using these methods: 1) past subjects that indicated they wanted to be contacted about future studies will be called by study staff to elicit their interest in this study, and 2) the PI will refer potential subjects from her UAMS clinic population to study staff who will then contact the referrals via phone. Once a potential subject has agreed to come to UAMS for an informed consent discussion, an appointment will be made for them to meet with study staff in the research area of the 3rd floor of the Reynolds Institute at UAMS. This study will enroll up to 80 subjects aged 60-89 years inclusive.

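### Section 3.2 drops subjects after randomisation and Sections 7.1-7.5 name no analysis population or missing-data handling, so the Visit 14 comparison appears to rest on those who stayed

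*Combined protocol and SAP*

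**What the plan says.** Section 3.1 places randomisation at Visit 2 ("Randomization will be performed as mentioned below"), before any weekly product visit. Section 3.2 then sets two grounds for removal: consistently reported intake below 80%, or a subject who "fails to show up for the weekly visit multiple times, they will be dropped from the study". Neither consistent low intake nor the number of missed visits is quantified.

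After baseline, strength, 6-minute walk and SF-36 are measured only at Visits 8 and 14 (Table of Events; Section 3.1). Visit 14 is the last contact ("At the end of this visit, subject will have no further study visits"). No assessment is described for a subject who has been dropped.

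Section 3.0 says that up to 80 subjects "will be enrolled to obtain 60 completers (30 per group"), Section 4.0 repeats the ceiling ("This study will enroll up to 80 subjects aged 60-89 years inclusive"), and Section 7.3 sizes the trial on 60 completed subjects. Section 7.1 specifies a repeated-measures ANCOVA tested at 5%, with baseline, lean body mass and gender in the model. If the interaction is significant, Section 7.2 moves to a separate ANCOVA at the midpoint and at the final visit, tested at 2.5%. Sections 7.1-7.5 do not say who is analysed or what is done when an outcome is missing.

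**The concern.** The rule removes people from the study, not only from product, and it acts on behaviour after randomisation. If their Visit 14 outcomes are not collected, no later analysis can recover them, and the final comparison is between those in each arm who kept taking product and attending. Randomisation does not protect that comparison when the reasons for loss relate to outcome and operate differently in the two arms.

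Different loss by arm is possible: Section 3.5 concedes a difference between the products ("Although the study products differ in taste"), and the Appendix shows that they differ in content. The documents contain no adherence data that would show it happens.

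A second consequence is that, with no population named, the question of who counts can be settled after the data are seen.

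**Working it through.** **1. The plan's own power.** Inputs from Table 4: mean changes 105.1, 11.0, 4.1 and 0.23; SDs 89.3, 13.3, 4.6 and 0.28; 30 per arm; alpha 2.5%. The effect sizes are d = 105.1/89.3 = 1.177, 11.0/13.3 = 0.827, 4.1/4.6 = 0.891 and 0.23/0.28 = 0.821. A two-sided two-sample t-test (noncentral t, noncentrality d × √(n/2)) gives 98.7%, 81.4%, 87.2% and 80.8%, against 98.67%, 81.31%, 87.19% and 80.80% in the table. The plan's power therefore reproduces with 30 per arm, which Sections 3.0 and 7.3 define as completers.

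**2. Bias from unequal loss (illustration; every input is assumed).** Suppose there is no true effect, 40 are randomised per arm, there is no baseline adjustment, and a subject is lost when a standard normal driver falls in its lowest fraction L. Let r be the correlation of the driver with outcome. The mean driver among those kept is m(L) = φ(z)/(1 − L), where z is the L-quantile. The bias is r × [m(L₁) − m(L₂)].
- 35% v 15%: m = 0.570 and 0.274, difference 0.296. With r = 0.2, 0.3 and 0.5 the bias is 0.059, 0.089 and 0.148 SD. On the Table 4 SD for 6-minute walk this is 5.3 (r = 0.2) to 13.2 (r = 0.5).
- 30% v 20%: m = 0.497 and 0.350, difference 0.147. The bias is 0.029, 0.044 and 0.073 SD.
- Equal loss with the same driver: 0.

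Simulated type I error for 35% v 15% with r from 0.2 to 0.5 is about 3% to 5% at the 2.5% level (separate runs lie between 2.7% and 5.1%) and about 5.5% to 9.1% at the 5% level.

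**3. Would Visit 8 data cure it?** Take r = 0.5 with both visits and the 35% v 15% case, and suppose every lost subject has a Visit 8 value (the best case). Regressing Visit 14 on Visit 8 among those kept has slope b = (ρ − r²c)/(1 − r²c), where c = m(m − z) is 0.544 and 0.360 in the two arms. The remaining bias is r × [m₁(1 − b₁) − m₂(1 − b₂)]. At ρ = 0.50, b = 0.421 and 0.451, so the result is 0.5 × (0.570 × 0.579 − 0.274 × 0.549) = 0.090 SD. At the other Table 5 correlations, 0.25 and 0.75, it is 0.134 and 0.045, all against 0.148 without Visit 8 data. The midpoint values help, but only in part.

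**4. Power if all randomised subjects are analysed.** Assume 40 per arm, all measured, with 25% of the active arm non-adherent and gaining nothing. The mean effect is 0.75d and the active-arm variance is 1 + 0.25 × 0.75 × d². For leg strength: 0.75 × 0.827 = 0.620; variance 1.128; pooled SD √[(1 + 1.128)/2] = 1.032; effective size 0.601; noncentrality 0.601 × √20 = 2.69.

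| Endpoint | 30 completers, 2.5% | 40 per arm, diluted, 2.5% | 40 per arm, diluted, 5% |
|---|---|---|---|
| 6-minute walk | 98.7% | 92% | 96% |
| Leg strength | 81% | 66% | 76% |
| Grip strength | 87% | 72% | 81% |
| Gait speed | 81% | 65% | 75% |

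If the non-adherent quarter keeps half the benefit, power at 2.5% is about 99%, 82% and 88% for the first three endpoints, no lower than for 30 completers.

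**The case against.** **The model may already use partial data.** A repeated-measures model fitted by likelihood would include Visit 8 values from later drop-outs, and nothing excludes them. A reader might infer that the whole arm comparison is one of completers; the documents do not support that for the midpoint. What stands is that Section 7.1 does not say the model works this way, and the separate final-visit ANCOVA in Section 7.2 has no outcome for a subject without Visit 14.

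**Non-collection is not stated.** Correct. It is inferred from the word dropped and from the absence of any provision for follow-up. The sentence closing Visit 14 describes attenders and is silent on dropped subjects.

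**Covariates absorb part of the bias.** Section 7.1 adjusts for baseline, lean body mass and gender. Loss driven by initial frailty would be partly corrected, so the unadjusted figures may be too high.

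**Blinding protects the choice of population.** Section 3.5 breaks the blind after data entry; Section 3.6 keeps the code "known only to the unblinded study staff until blinding has been broken at the end of data analysis". Either limits choosing a population by known arm. Neither defines a population or supplies missing outcomes.

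**The sponsor may want the effect in adherers.** Hypothesis 2 and, for 12 weeks, Hypothesis 1 speak of regular consumption. But no such target is stated in the analysis sections, and comparing those who stayed does not estimate it with the protection of randomisation.

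**Conclusion.** The point holds as a gap in the plan that should be fixed. The text is clear on three matters: the drop rule acts after randomisation, no later assessment is provided, and no population or missing-data handling is named. That the Visit 14 comparison rests on those who stayed is a well-founded inference.

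The size of any bias is unknown and may be zero. The 0.06-0.15 SD range rests on assumed loss rates and correlations, without baseline adjustment, and Section 3.2 would cause only part of any loss. The 2.5% level applies only after a significant interaction, which Section 7.3 treats as the worst case.

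Two stronger readings are not supported. A reader might take 60 of 80 as a planned 25% loss after randomisation; the 80 may include subjects who fail screening after consent at Visit 1, and no loss rate is given. A reader might also infer that an as-randomised analysis cannot be adequately powered within 80 subjects. Under the dilution assumed above, leg and grip strength fall below 80% at the 2.5% level, but grip reaches about 81% at 5%, and 6-minute walk exceeds 90% at both.

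**What to change.** 1. **Section 3.2:** separate stopping study product from leaving the study. Invite every randomised subject who has not withdrawn consent to the Visit 8 and Visit 14 outcome assessments, whatever their adherence. When product should be stopped is left to the sponsor.
2. **Section 7.1:** make the primary analysis as-randomised, using all available post-baseline data, including Visit 8 values from later drop-outs. Add a sensitivity analysis for subjects missing Visit 14 (for example, multiple imputation with a range of shifts by arm). Keep an adherent-completer analysis as supplementary.
3. **Section 7.3:** state how many subjects will be randomised and restate power for this analysis. As an editorial matter, the Table 4 caption should call its 60 subjects completed, not enrolled.

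**Cost:** protocol wording, and two assessments that are already scheduled, each carrying $50 in Section 3.3. The effect may be diluted and the stated power less favourable, as in the table above. Some subjects dropped for missed visits may still not attend, so the change will not recover every outcome.

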Dispense study product and diary		x	x	x	x	x	x	x	x	x	x	x	x	
Return study product and diary			x	x	x	x	x	x	x	x	x	x	x	x

¹ For criteria-related testing.² Can be done on visit 1 or 2.³ Between visits, at home. Calls will be made to remind subjects of the time for collection.⁴ For protocol endpoints.

⁵ If subjects unable to provide at this visit, they can take home a collection kit to return at next visit.

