6.0 Data Handling and Recordkeeping

Source documents and CRFs will be stored in a secure area of the PI's laboratory. Access will be limited to study personnel. Documents containing identifiers (except the signed ICF) will be destroyed by shredding approximately 7 years after data analysis is completed or publication of data; whichever is longest. The original, signed ICF will be kept indefinitely. At no time shall Protected Health Information be released to non-study personnel.

The Principal Investigator will carefully monitor study procedures to protect the safety of research subjects, the quality of the data and the integrity of the study. All study subject

material will be assigned a unique identifying code or number. The key to the code (the instrument associating the data with subject identity) will be kept on a password-protected UAMS server, located behind locked doors in a restricted access area of the UAMS campus. Only those individuals listed on the title page of this protocol and their research staff members will have access to the code and information that identifies the subject in this study. This file will be deleted approximately 7 years after data analysis is completed.

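### Adverse events are asked about only at attended visits, and the protocol states no safety contact for subjects who stop attending or are dropped

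*Combined protocol and SAP*

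**What the plan says.** Section 3.1 has subjects questioned in person at every visit from Visit 2 to Visit 14. The usual wording is "They will be asked about any adverse events since last visit". The Table of Events has no adverse-event row and no withdrawal visit.

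Section 3.2 sets two grounds for removal: consistently reporting less than 80% intake, and repeated absence. On the second it says that a subject who "fails to show up for the weekly visit multiple times, they will be dropped from the study". It gives no further step for either group.

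The only on-study telephone contact is in footnote 3 of the Table of Events and concerns urine: "Calls will be made to remind subjects of the time for collection". The medical record is used at Visit 1, for history, medications and recent eligibility results. Section 6.0 makes a general commitment, "The Principal Investigator will carefully monitor study procedures to protect the safety of research subjects", and Section 8.0 promises compliance with regulations and institutional policy. Neither describes how an event would be learned of in someone who no longer attends.

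Section 1.0 gives the background risk: "The risk of death is 35% in the first year after diagnosis, and decreases to about 10% per year thereafter".

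**The concern.** The events that matter most for safety are among those most likely to stop a person coming back. If the only enquiry is made at a visit, a subject who dies, or is admitted and never returns, gives no answer. The drop rule then makes the silence permanent.

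Two things are at stake. First, any summary of harms by arm made from the collected data would be incomplete in a way that can depend on the harm itself. Second, the protocol assigns nobody in writing to find out why a heart-failure patient aged 60 to 89 has stopped attending.

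**Working it through.** The plan gives no figure on this point, so the main check is a reading of the text, followed by a short calculation for scale.

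**Step 1. Which events does the stated procedure reach?**

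- *Absent for a time, then returns before being dropped.* Reached. The question covers the whole interval since the last visit.
- *Dropped for low intake.* Largely reached up to that point. Low intake would normally be reported at an attended visit, where adverse events are also asked about. Nothing is stated for the time afterwards.
- *Dropped for repeated absence.* Not reached from the last attended visit onward. No closing question is stated.
- *Death, or a hospital stay that ends attendance.* Not reached. There is no later visit at which to ask.

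**Step 2. Is there another stated route?** The urine calls are reminders. The recruitment calls in Section 4.0 come before consent. Record use is described at Visit 1 only. Sections 6.0 and 8.0 are general. I found no text that supplies a route.

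**Step 3. How many subjects could leave this way?** Section 3.0 enrols up to 80 to obtain 60 completers, so at most 80 − 60 = 20 (20/80 = 25%). Consent and screening are at Visit 1 and randomisation is at Visit 2, so some or all of the 20 could be screen failures. The number of randomised subjects lost is therefore somewhere from 0 to 20.

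**Step 4. Scale of the background risk (context only).** Assume a constant hazard. For annual risk r, the 12-week risk is 1 − (1 − r)^(12/52).

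| Annual risk | 12-week risk | Deaths in 60 | Deaths in 80 |
|---|---|---|---|
| 10% (Section 1.0, after year one) | 1 − 0.90^(12/52) = 2.40% | 1.44 | 1.92 |
| 5% (assumed, half) | 1 − 0.95^(12/52) = 1.18% | 0.71 | 0.94 |

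The 10% figure is probably high for this sample, because Section 4.2 excludes recent infarction, unstable angina, end-of-life palliative care and medical instability. Recent diagnosis is not itself an exclusion, but the documents do not say how many subjects would be in their first year, so I do not use the 35% figure. No hospital-admission rate is given.

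**The case against.** The strongest reply is that this argues from silence. Section 4.0 draws subjects from past participants and the principal investigator's own clinic. Records can be printed for the institution's patients. The study runs under ethics-board oversight and institutional policy. The consent pages, which may carry reporting instructions, are not in the available text. Staff could well hear of a death. This stands as a limit: the text supports only that no means is stated, not that none exists. It does not remove the point, because none of these is a written follow-up procedure.

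A second reply is that no harms hypothesis or harms analysis exists, so no planned analysis is harmed. That is true. The point concerns the completeness of safety data and the care of subjects.

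A reader might also infer stronger things that the documents do not support:

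- *That an unrecorded death is likely.* At 10% per year the chance of at least one death in 60 is 1 − (1 − 0.0240)^60 = 77%. That is the chance that a death occurs, not that it goes unrecorded.
- *That a harms comparison could be wrong by a large, known amount.* With 40 randomised per arm and 10 lost from each, the difference could move by 10/40 = 25 points either way. That needs no screen failures, and an unrecorded event in every lost subject of one arm and in none of the other.
- *That dropped subjects keep taking product unobserved.* At Visit 2, "Study staff will dispense approximately 10 days" of product, and a 200 g container lasts 200/(9 × 2) = 11.1 days. A drop for absence needs at least two missed weekly visits, or about 14 days, so supplies would mostly be used up first unless leftovers had built up.

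**Conclusion.** The point holds in limited form. As written, the protocol asks about adverse events only at attended visits. It ends participation for repeated absence or low intake, and states no safety contact afterwards. An event that permanently ends attendance, or that follows a drop, has no stated means of being recorded.

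The number of such events, and any difference between arms, cannot be found from the documents. The 1.4 deaths in 60 only shows that serious events within 12 weeks are foreseeable in this population. It rests on a constant hazard and a general heart-failure rate. Sample size, power and the efficacy tests are untouched, and a reader should not take this as a reason to doubt them. The change is worth making because a written rule ends safety observation in older heart-failure patients and is cheap to replace.

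**What to change.** 1. In Section 3.2, replace removal from the study with this rule: the subject stops study product but remains in safety follow-up through week 12, unless consent to contact is withdrawn.
2. Phone each randomised subject who stops, or who misses two consecutive weekly visits, at that point and again at week 12. For those who return, Visit 14 replaces the second call.
3. If the subject is not reached, contact a next of kin or alternate contact for whom consent was given, and check the UAMS medical record where available. Calls to the subject alone cannot capture a death and may miss a long admission.
4. Record adverse events, hospital stay, vital status and reason for stopping. In Section 7, report these by arm for all randomised subjects who took any product, with the number not reached.

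**Cost.** A protocol amendment, a few case report form fields and one table. Planned contacts are at most 2 × 20 = 40 for non-completers, plus 6 to 12 for completers who miss two visits in a row (assuming 10% to 20% of 60). That is 46 to 52, or roughly 50, before repeat attempts. Some subjects will still not be reached, and telephone reports are less complete than visits.
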